a

## STATEMENT OF COMPLIANCE

The trial will be carried out in accordance with International Conference on Harmonisation Good Clinical Practice (ICH GCP) and the following:

- United States (US) Code of Federal Regulations (CFR) applicable to clinical studies (45 CFR Part 46, 21 CFR Part 50, 21 CFR Part 56, 21 CFR Part 312, and/or 21 CFR Part 812)

The protocol, informed consent form, recruitment materials, and all participant materials will be submitted to the Institutional Review Board (IRB) for review and approval. Approval of both the protocol and the consent form must be obtained before any participant is enrolled. Any amendment to the protocol will require review and approval by the IRB before the changes are implemented to the study. In addition, all changes to the consent form will be IRB-approved; a determination will be made regarding whether a new consent needs to be obtained from participants who provided consent, using a previously approved consent form.

## 1 PROTOCOL SUMMARY

### 1.1 PROTOCOL SYNOPSIS

**Study Title:** Le Rêve 3.0: A Double-Blind, Placebo-Controlled, Randomized, Crossover Investigational Study to Determine if Defined CBD, a Custom-Formulated Cannabidiol (CBD) Capsule, Influences Sleep Physiology.

**Study Description:** Insomnia is a disorder in which people have inadequate or poor-quality sleep due to a number of factors, such as difficulty falling asleep, waking up frequently during the night with difficulty returning to sleep, waking up too early in the morning, or having unrefreshing sleep. Defined CBD is a capsule composed of highly purified (>99.9% purity) hemp-derived CBD and terpenes (>98% purity). Defined CBD contains no  $\Delta$ -9-tetrahydrocannabinol ( $\Delta$ -9-THC). Our research study, entitled Le Rêve 3.0, is designed to evaluate the efficacy of Defined CBD on sleep physiology. This trial is not intended to treat, diagnose, prevent, or cure any disease.

**Objectives:** Primary Objectives: To determine if Defined CBD influences objective measures of sleep physiology.

[figure not shown]
Secondary Objectives: To determine if Defined CBD influences subjective measures of sleep physiology.

**Endpoints:** Primary Endpoint: The percentage of sleep spent in deep [slow wave sleep (SWS)] and rapid eye movement (REM) sleep as determined using an objective wrist-worn sleep-tracking device called Whoop.

Secondary Endpoints: Total sleep time, sleep latency, the number of sleep disturbances, time spent in each sleep stage, percentage of time spent in each sleep stage, and subjective measures of sleep physiology as collected via participant surveys.

Study Population:	We will enroll 150 study participants who display chronic insomnia defined as a self-reported difficulty initiating (latency to persistent sleep >30 min) and/or maintaining sleep (>30 min awake, or waking >30 min before desired waking time) on three or more nights per week for at least 3 months. Participants will also complete a brief clinically validated insomnia severity index, and only participants with an Insomnia Severity Index score >15 will be enrolled in Le Rêve 3.0. We will enroll males or females aged 25–70 years that are located in the United States that meet inclusion and exclusion criteria.
Phase:	N/A
Description of Sites/Facilities Enrolling Participants:	Le Rêve 3.0 will be a decentralized study completed by participants in the comfort of their own homes. Recruitment, enrollment, informed consent, and distribution of study materials to participants will all be managed by the contract research organization (CRO) 83 Bar, Inc.
Description of Study Interventions:	Study interventions will include Defined CBD or a placebo control that will be taken orally (p.o.) as two small capsules one hour prior to going to bed. Defined CBD is a capsule made to GMP standards composed of vegetable cellulose (gluten-free, non-GMO, vegan, certified kosher, certified halal) that contains 300 mg >99.9% purity hemp-derived CBD made in a GMP-certified laboratory that is dissolved in coconut oil (USDA certified organic, non-GMO, dairy-free, gluten-free, vegan coconut oil). Defined CBD is a custom chemical formulation that also contains low concentrations (1 mg each) of highly purified (>98% purity) forms of the terpenes linalool, myrcene, phytol, limonene, $\alpha$ -terpinene, $\alpha$ -terpineol, $\alpha$ -pinene, and $\beta$ -caryophyllene [Food Grade (GRAS), Natural, Organic, non-GMO, dairy-free, gluten-free, vegan] made in GMP-certified laboratories. Defined CBD contains no $\Delta$ -9-tetrahydrocannabinol ( $\Delta$ -9-THC). The safety of CBD  and these terpenes  at the doses found in Defined CBD is well established.
Study Duration:	The estimated time from when Le Rêve 3.0 opens enrollment until completion of data analyses will be 20 weeks.
Participant Duration:	After enrollment, the participant duration for the entire study will be 12 weeks.

## 1.2 SCHEMA

### 1.3 SCHEDULE OF ACTIVITIES (SOA)

Procedures	Screening Weeks -4 to -1	Enrollment Day 1	Collect Baseline Data Weeks 1-2	Treatment 1 Weeks 3-6	Treatment Washout Week 7	Treatment 2 Weeks 8-11	Treatment Washout Week 12	Post-Treatment Weeks 13-20
Informed consent	X							
Medical history	X							
Randomization				X				
Administer study intervention				X		X		
Adverse event review and evaluation								X

## 2 INTRODUCTION

### 2.1 STUDY RATIONALE

Insomnia is a disorder in which people have inadequate or poor-quality sleep due to a number of factors, such as difficulty falling asleep, waking up frequently during the night with difficulty returning to sleep, waking up too early in the morning, or having unrefreshing sleep. The majority of over-the-counter (OTC) supplements used to treat insomnia (e.g. melatonin, valerian root, lavender) have limited efficacy, while the best-selling prescription drugs for insomnia (e.g. Ambien, Halcion, Sonata, Lunesta) have serious and undesirable side effect profiles that limit their utility. There is a strong scientific rationale to support the hypothesis that CBD might positively impact sleep physiology, and our study, entitled Le Rêve 3.0, is designed to fill that void in knowledge.

### 2.2 BACKGROUND

A survey of 1,267 adults by Consumer Reports indicates that nearly 80% of Americans have trouble sleeping at least once a week. Insomnia is the most common sleep disorder and is an established risk factor for anxiety, depression and other diseases. Insomnia is defined clinically as the perception or complaint of inadequate or poor-quality sleep due to a number of factors, such as difficulty falling asleep, waking up frequently during the night with difficulty returning to sleep, waking up too early in the morning, or having unrefreshing sleep. Insomnia causes significant distress and/or impairment in daytime functioning in people who suffer from it. The prevalence rates of clinically diagnosed insomnia have increased in recent years to ~19% of the adult U.S. population, representing ~46 million. Some studies suggest that the rate of undiagnosed insomnia in the US may be as high as 25% (~80 million).

CBD is the active ingredient of Epidiolex®, a drug approved by the FDA in 2018 for the treatment of seizures associated with two rare and severe forms of epilepsy, Lennox-Gastaut syndrome (LGS) and Dravet syndrome (DS). In 2018, the U.S. congress passed the Hemp Farming Act of 2018 (the Farm Bill), which removed remove hemp (defined as cannabis with less than 0.3% THC) from Schedule I controlled substances, and made it an ordinary agricultural commodity. This Bill immediately led to the widespread purification, sale and interstate commerce of CBD, a molecule obtained from hemp (~\$4.7 billion in U.S. sales in 2021). The result has been that storefronts and online retailers have flooded the market with CBD products, many with unsubstantiated therapeutic claims. Sadly, U.S. consumers are currently using

CBD to treat a variety of ailments in the absence of rigorous clinical studies. Indeed, ~14% of the U.S. adult population (~29 million adults) admit to using CBD (Gallup Survey, U.S. News & World Report). Nonetheless, rigorous clinical research on products that contain CBD is desperately lacking. Our research study aims to test the effects of a Defined CBD, a capsule with high purity (>99.9%) CBD, on the structure and function of sleep physiology.

There is a strong scientific rationale to test a CBD-based product on sleep physiology in a properly controlled, well-powered and rigorous study in humans. Preclinical studies in rats indicate CBD increases total sleep time in a dose-dependent manner. In one early but small (N = 10) placebo-controlled clinical study in Brazil, subjects with insomnia that received 160 mg of CBD reported having slept significantly more than those who had been given a placebo control. However, the study was only performed in an extremely small number of subjects, and did not use any objective measures of sleep physiology. More recently, a larger study in 72 adults with clinically diagnosed anxiety, CBD (25-75 mg/day) improved sleep in 66% of the patients as determined by a sleep quality questionnaire [the Pittsburgh Sleep Quality Index (PSQI)]. However, this was an open label study (i.e. not blinded), lacked a placebo-control, and also did not include any objective measures of sleep physiology. As such, no strong scientific conclusions regarding causality can be drawn from the clinical data.

In a survey by Consumer Reports, ~45% of adults who reported trying CBD said they used it to help them sleep, and a majority of those people said they believed that it worked. Nonetheless, to this date a rigorous, properly-controlled, and well-powered study to determine if CBD influences sleep physiology has simply never been reported in the scientific literature. The Le Rêve 3.0 study is designed to fill this important void in scientific knowledge.

We hypothesize that a novel CBD-based formulation in the form of an orally administered capsule will positively impact sleep physiology metrics in subjects with insomnia, as determined using an objective sleep-tracking device called “Whoop”. The capsule we will test is composed of >99.9% purity hemp-derived CBD with a custom chemical formulation that also contains low concentrations (1 mg each) of highly purified (>98%) forms of the terpenes linalool, myrcene, phytol, limonene,  $\alpha$ -terpinene,  $\alpha$ -terpineol,  $\alpha$ -pinene, and  $\beta$ -caryophyllene. Preclinical studies in animals have shown that these terpenes are sedating, but their potential effects on sleep physiology in humans have not been established. The capsules do not contain any  $\Delta$ -9-THC.

## 2.3 RISK/BENEFIT ASSESSMENT

### 2.3.1 KNOWN POTENTIAL RISKS

Based on a large amount of published clinical data, the World Health Organization (WHO) has established that CBD (the active ingredient in Defined CBD) is non-intoxicating and has an excellent safety profile in humans. Previous clinical studies indicate that adverse reactions with CBD are rare. The most common adverse reactions that occurred with CBD when given at a high dose [e.g., at the recommended dose for the FDA approved CBD drug Epidiolex® (20 mg/kg/day)], were somnolence (sleepiness); decreased appetite; diarrhea; transaminase elevations; fatigue; malaise; asthenia (abnormal physical weakness or lack of energy); rash; insomnia; sleep disorder; poor quality sleep; and infections. However, these adverse reactions were only observed in <15% of patients at a CBD dose (20 mg/kg/day or ~1,800 mg for a 90 kg male) that is approximately six times greater than the dose that will be used in Le Rêve 3.0 study (300 mg or ~3 mg/kg/day for a 90 kg male) (see supplemental file with Epidiolex® Safety Information). Moreover, the frequency of these adverse events decreased significantly when Epidiolex® was administered at a lower dose (10 mg/kg/day or ~900 mg for a 90 kg male), a dose that is still three times greater than the dose we will use in Le Rêve 3.0. A recent meta-analysis of AEs

from 12 clinical trials with CBD indicated that associations with abnormal liver function tests, somnolence, sedation and pneumonia were limited *exclusively* to childhood epilepsy studies, where CBD may have interacted with other medications such as clobazam and/or sodium valproate. After excluding studies in childhood epilepsy, the only adverse outcome associated with CBD treatment was diarrhea. And, again, this was only observed at doses well above the CBD dose that will be evaluated in Le Rêve 3.0. Therefore, due to the low dose of CBD that will be tested in Le Rêve 3.0 (300 mg p.o.), if AEs are observed with Defined CBD, we presume that they will be minor and occur at a lower frequency than what was observed in previous clinical studies.

Although rare, some adults display hypersensitivity to CBD. Participants with known hypersensitivity to CBD will be excluded from participating in Le Rêve 3.0. As noted above, some recent studies indicate that extremely high doses of CBD (much higher than what will be used in Le Rêve 3.0) might impair liver function. Therefore, as a precaution, study participants in Le Rêve 3.0 will be required to refrain from the use of any of the following contra-indicated drugs for at least one week prior to and for the duration of the study: erythromycin, clarithromycin, itraconazole, ketoconazole, posaconazole, voriconazole, ritonavir, telaprevir, boceprevir, amlodipine, gemfibrozil, cyclosporine, danazol, amiodarone, verapamil, diltiazem, rifampin, theophylline, tizanidine, bupropion, efavirenz, diflunisal, propofol, fenofibrate, lamotrigine, morphine, lorazepam, diazepam, clobazam, stiripentol, valproate, everolimus, sirolimus, or tacrolimus, and niacin (vitamin B3 greater than 1g/ day). Participants who cannot refrain from the intake of these contra-indicated drugs prior to and throughout the study will be excluded from participating in Le Rêve 3.0.

Defined CBD also contains low concentrations (1 mg each) of highly purified (>98%) forms of the terpenes linalool, myrcene, phytol, limonene,  $\alpha$ -terpinene,  $\alpha$ -terpineol,  $\alpha$ -pinene, and  $\beta$ -caryophyllene. Terpenes are widely used as fragrances and flavors in consumer products such as perfumes, cosmetics and cleaning products, as well as food and drink products. For example, the aroma and flavor of hops comes, in part, from sesquiterpenes (mainly  $\alpha$ -humulene and  $\beta$ -caryophyllene), which are used to make beer. Importantly, the terpenes in Defined CBD are designated by the FDA as GRAS (Generally Regarded as Safe) for oral consumption. Although rare, some adults display mild skin allergies to terpenes when applied topically. As a precaution, participants with known hypersensitivity to terpenes will be excluded from participating in Le Rêve 3.0.

Defined Research confirms the molecular composition of every batch of Defined CBD (including the Defined CBD to be used in Le Rêve 3.0) by an ISO-10725-accredited analytical testing laboratory. These analytical tests confirm the concentration and purity of Defined CBD, and ensure that it is free from any contaminants, including pesticides, residual solvents and heavy metals. Electronic records that document these lab tests are stored at Defined Research and are available upon request.

### 2.3.2 KNOWN POTENTIAL BENEFITS

Epidiolex® is indicated for the treatment of seizures associated with Lennox-Gastaut syndrome, Dravet syndrome, or tuberous sclerosis complex in patients 1 year of age and older. Given that the most common adverse reaction in patients treated with Epidiolex® is somnolence, one potential benefit that study participants may receive in Le Rêve 3.0 when treated with Defined CBD is a change in their sleep physiology that increases their somnolence. Several clinical studies indicate that CBD can decrease acute anxiety. Participants with social anxiety disorder and controls were blindly allocated to receive CBD or a placebo control before a simulation public speaking test. CBD resulted in significantly reduced anxiety, cognitive impairment and discomfort, and significantly decreased hyper-alertness in anticipatory speech.  $\Delta$ -9-THC is well established as having anxiogenic (anxiety-promoting) properties in clinical studies, and these effects can be blocked by CBD. Therefore, as some clinical studies indicate that CBD

may decrease acute anxiety, it is also possible that study participants in Le Rêve 3.0 treated with Defined CBD might feel less anxious.

---

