### 6.4 STUDY INTERVENTION COMPLIANCE

Adherence to the protocol by study participants will be assessed by two independent approaches. In the first approach, a CBD Sleep Study team member will be checking Whoop data (stored on the cloud)

on a daily basis for each participant to ensure that the data is being collected consistently and accurately. In the second approach, study participants will be required to answer a text (SMS) message on a daily basis to confirm whether or not they took the study treatment.

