**8.2.4** Based on a large amount of published clinical data, the World Health Organization (WHO) has established that CBD (the active ingredient in Defined CBD) is non-intoxicating and has an excellent safety profile in humans. Previous clinical studies indicate that adverse reactions with CBD are rare. The most common adverse reactions that occurred with CBD when given at a high dose [e.g., at the recommended dose for the FDA approved CBD drug Epidiolex® (20 mg/kg/day), were somnolence (sleepiness); decreased appetite; diarrhea; transaminase elevations; fatigue; malaise; asthenia (abnormal physical weakness or lack of energy); rash; insomnia; sleep disorder; poor quality sleep; and infections. However, these adverse reactions were only observed in >10% of patients at a CBD dose (20 mg/kg/day or ~1,800 mg for a 90 kg male) that is approximately six times greater than the dose that will be used in Le Rêve 3.0 study (300 mg or ~3 mg/kg/day for a 90 kg male). Moreover, the frequency of these adverse events decreased significantly when Epidiolex® was administered at a lower dose (10 mg/kg/day or ~900 mg for a 90 kg male), that is still three times the dose we will use in Le Rêve 3.0. A recent meta-analysis of adverse events from 12 clinical trials with CBD indicated that associations with abnormal liver function tests, somnolence, sedation and pneumonia were limited to childhood epilepsy studies, where CBD may have interacted with other medications such as clobazam and/or sodium valproate. After excluding studies in childhood epilepsy, the only adverse outcome associated with CBD treatment was diarrhea. And, again, this was only observed at doses well above the CBD dose that will be evaluated in Le Rêve 3.0. Therefore, if adverse events are observed with Defined CBD in Le Rêve 3.0, we presume that they will be minor and only occur at a lower frequency than what was observed in previous clinical studies.

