## 8.3 ADVERSE EVENTS AND SERIOUS ADVERSE EVENTS

### 8.3.1 DEFINITION OF ADVERSE EVENTS (AE)

An adverse event (AE) is any untoward medical occurrence in a clinical study participant administered an investigational product, which does not necessarily have a causal relationship with the treatment. An AE can therefore be any unfavorable and/or unintended sign, symptom, or disease temporally associated with the use of an investigational product, whether or not considered related to the investigational product. AEs may also include pre- or post-treatment complications that occur as a result of protocol specified procedures or special situations (Section 8.3.8).

An AE does not include the following:

- Medical or surgical procedures such as surgery, endoscopy, tooth extraction, and transfusion. The condition that led to the procedure may be an adverse event and must be reported.
- Preexisting diseases, conditions, or laboratory abnormalities present or detected before the screening visit that do not worsen.
- Situations where an untoward medical consequence has not occurred (e.g. hospitalization for elective surgery, social and/or convenience admissions).
- Overdose without clinical sequelae (Section 8.3.8).
- Any medical condition or clinically significant laboratory abnormality with an onset date before the consent form is signed and not related to a protocol-associated procedure is not an AE. It is considered to be preexisting and should be documented as medical history.

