### 8.3.4 TIME PERIOD AND FREQUENCY FOR EVENT ASSESSMENT AND FOLLOW-UP

The occurrence of an AE or SAE may come to the attention of study personnel during interviews of a study participant presenting for medical care, or upon review by a study monitor.

All AEs including local and systemic reactions not meeting the criteria for SAEs will be captured on the appropriate electronic case report form (eCRF). Information to be collected includes event description, time of onset, medical monitor's assessment of severity, relationship to study product, and time of resolution/stabilization of the event. All AEs occurring while on study must be documented appropriately regardless of relationship. All AEs will be followed to adequate resolution.

Any medical condition that is present at the time that the participant is screened will be considered as baseline and not reported as an AE. However, if the study participant's baseline medical condition worsens at any time during the study, it will be recorded as an AE.

Changes in the severity of an AE will be documented to allow an assessment of the duration of the event at each level of severity to be performed. AEs characterized as intermittent require documentation of onset and duration of each episode.

The medical monitor will record all reportable events (AEs and SAEs) starting with the first day of the study until the study is completed. The medical monitor will follow up with the study participant up to three times until resolution or stabilization.

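### Somnolence is named both a benefit and a leading adverse reaction, and no section says how sleepiness is classified or asked about, so it is likely to be recorded inconsistently and under-counted in both periods

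*Combined protocol and SAP*

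**What the plan says.** Section 2.3.2 (Known Potential Benefits) starts its argument with "Given that the most common adverse reaction in patients treated with" the approved CBD drug. It identifies that reaction as somnolence and concludes that a possible benefit to participants "is a change in their sleep physiology that increases their somnolence".

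Section 8.2.4 says that the most common adverse reactions at 20 mg/kg/day, about six times the trial dose, "were somnolence (sleepiness); decreased appetite; diarrhea; transaminase elevations; fatigue", followed by others. It then cites a meta-analysis of 12 trials in which "associations with abnormal liver function tests, somnolence, sedation and pneumonia were limited to childhood epilepsy studies". Section 2.3.1 says the same on both points. Section 8.3.3.3 makes 8.2.4 the reference for whether an AE is expected.

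Section 8.3.1 defines an AE as an untoward medical occurrence, which can be "any unfavorable and/or unintended sign, symptom, or disease temporally associated with the use of an investigational product". Section 8.3.4 adds: "All AEs occurring while on study must be documented appropriately regardless of relationship". It also treats a condition present at screening as baseline, not an AE, unless it worsens. Section 8.3.5 sends all AEs after the start of treatment to the eCRF.

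On capture, 10.1.7 gives the daily text two jobs: checking compliance and picking up AEs and SAEs. Section 6.4 describes that text only as asking participants "to confirm whether or not they took the study treatment". Under inclusion criterion 5 in 5.1, the texts run daily for the whole study.

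**The concern.** Whether sleepiness after a bedtime dose counts as the hoped-for effect or as an AE is left to whoever reads the report. The protocol names the effect as a benefit in one place and an adverse reaction in two others. The AE definition depends on whether the effect is unfavorable or unintended, which is exactly what the two labels leave open. Two equally careful readers could classify the same message differently.

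No described procedure would make up for this. No question about sleepiness is specified, at baseline or on treatment. Section 8.3.4 otherwise relies on participants presenting for medical care or on a monitor's review, and mild next-day sleepiness would seldom surface either way. At stake is how far a finding of few AEs, or of little difference in sleepiness, can be trusted for an effect that the protocol itself links to CBD.

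**Working it through.** The plan gives no somnolence rate at the trial dose and no target for AE detection, so there is no figure to reproduce. The check is a comparison of passages, followed by an illustration on assumed rates.

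**Step 1: labels.** Section 2.3.2 treats increased somnolence as a benefit that participants in this trial may receive. Sections 2.3.1 and 8.2.4 list it first among adverse reactions at a higher dose, then say the association was limited to childhood epilepsy studies. The first expects possible somnolence in adults at 300 mg. The others argue against expecting it. They do not fit together.

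**Step 2: classification.** Under 8.3.1 the test is unfavorable and/or unintended. Sleepiness that impairs the next day is unfavorable and qualifies. Sleepiness at bedtime, in people with insomnia who dose one hour before bed (6.1.2), may be neither. No section draws a line between the two. The rules in 8.3.3.3, 8.3.4 and 8.3.5 apply only once something has been judged an AE, so they do not settle the question.

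**Step 3: elicitation.** Section 10.1.7 relies on the daily text for AEs, but 6.4 gives its content as a dosing confirmation. No AE wording is given. The participant survey is completed only at the end of each four-week period (sections 3 and 8.1), and no daytime-sleepiness item is described. The schedule in 1.3, as extracted, marks AE review only under Weeks 13-20. That layout should be checked against the source table before anything is built on it.

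**Step 4: baseline.** The 8.3.4 rule needs a baseline level to judge worsening. No baseline measure of daytime sleepiness is planned, in a population that 2.2 describes as impaired in the daytime.

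**Step 5: size, on assumed inputs.** Let p1 and p0 be the true proportions with next-day sleepiness on CBD and on placebo, and c the fraction recorded. Participants and the PI are blinded (6.3), so take c as the same in both periods.

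- Recorded excess = c × (p1 − p0). Recorded ratio = (c × p1)/(c × p0) = p1/p0.
- Assume p1 = 10%, p0 = 4%, c = 0.5. These values are not from the documents.
- True excess: 10 − 4 = 6 points. Recorded: 0.5 × 10 = 5% v 0.5 × 4 = 2%, an excess of 3 points.
- Ratio: 10/4 = 2.5 before and 5/2 = 2.5 after.
- Range: with c anywhere from 1 down to 0, the recorded excess runs from 6 points to 0. Each tenth of reports lost removes 0.1 × 6 = 0.6 point.
- Among the 100 participants of the power statement in 9.2, that is 10 v 4 affected but 5 v 2 recorded.

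**Step 6: exposure.** The minimum is 4 nights × 4 weeks = 16 nights per treatment period for an adherent completer. It does not hold for everyone, because 9.2 allows for dropout of up to 33%.

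**The case against.** The case for leaving the text alone has four parts.

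- **Section 2.3.2 is background.** It tells no one how to classify an event, and its own sentence calls somnolence an adverse reaction. This stands, but no operating section supplies the missing rule.
- **The AE rules already cover unfavorable sleepiness.** The exclusions in 8.3.1 name neither somnolence nor intended effects, and listing in 8.2.4 makes somnolence an expected AE, not a non-AE. This stands. A reader might infer that staff may properly leave next-day sleepiness off the form. The documents do not support that, because impairing sleepiness meets the definition and must be recorded.
- **There is a capture route.** Section 10.1.7 names the daily texts, and the medical monitor records events. So it cannot be said that an impaired participant would fail to reach the monitor. What stands of the concern is that the route has no stated question.
- **Blinding protects the comparison.** A reader might infer that sleepiness would be discounted on CBD but kept on placebo, turning 10% v 4% into 5% v 4% in CBD's favour. That calculation halves one product only. Placebo capsules are described as identical in look, feel and smell (6.1.1), and participants and the PI are blinded (6.3). Selective loss would need recording to depend on something that differs by product, such as a correct guess at allocation, and the documents show nothing of the kind.

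Nor do the documents make somnolence the main expected harm at this dose: 2.3.1 and 8.2.4 say that, outside childhood epilepsy, diarrhea was the only adverse outcome associated with CBD.

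**Conclusion.** The concern holds as an unresolved classification combined with an unspecified question. It is neither an exclusion of somnolence from AE reporting nor a demonstrated bias between products. The likely consequence is inconsistent recording and some under-counting in both periods. That dilutes the absolute difference and leaves the ratio unchanged: 6 points becomes 3 in the illustration.

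This rests on three assumptions: the rates of 10% and 4%, the loss of half of reports, and equal loss in the two periods. The last assumes that whoever classifies events is blinded too. Section 6.3 names only the participants and the PI, and nothing suggests that the medical monitor knows the allocation. Under-recording itself is inferred from the text and not stated in it. Severity is minor to moderate: the primary endpoint is untouched, and the remedy is cheap.

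**What to change.** 1. Reconcile 2.3.2 with 2.3.1 and 8.2.4 on whether somnolence is anticipated in this trial, and limit the benefit stated in 2.3.2 to sleep at night.
2. Add one fixed yes/no item on daytime sleepiness to the existing daily text, with the same wording from baseline Weeks 1-2 through Week 12. Describe it in 6.4 and 10.1.7 so that the two sections agree on what the text asks.
3. In 8.3.1, state that daytime sleepiness that is new or worse than in the baseline weeks is recorded as an AE whatever its effect on night sleep. The reference to baseline keeps this consistent with 8.3.4. An unconditional rule would conflict with it.
4. In 9.4.4, tabulate the item by product against baseline.
5. Confirm when AE review takes place in the schedule in 1.3.

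The cost is a few sentences, one more text item per day and one more table. The downside is that more mild AEs will be recorded. A question asked identically in both periods replaces individual judgement and makes a low count believable.
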